# 8. Aims and objectives

#### 8a. Aim

To evaluate SL schemes for the private rented housing sector in England. The evaluation will assess health and social impacts, implementation and change mechanisms, and economic consequences.

# 8b. Objectives

WP1: To assess area and individual level impacts of SL schemes on health and social outcomes. To assess impacts on equity.

WP2: To assess SL in terms of the following (i) stakeholder acceptability (ii) pathways to impact, (iii) unintended and systemic consequences; (iv) barriers/facilitators; (v) equity assessment.

WP3: To assess whether SL schemes are value for money.

WP4: To share and interpret findings with stakeholders.

### **Research Question**

Can selective licensing (SL) schemes improve England's private rented housing sector leading to health and social benefits for residents?

#### **PICO**

- Population: Residents in areas exposed to SL; Individual PRS tenants exposed to SL. (For qualitative work, relevant stakeholders we will sample include tenants, landlords, implementers and service providers).
- Intervention: SL schemes.
- Control: Matched control areas.
- Outcomes:
  - Area level: mental health and wellbeing (SAMHI: primary outcome); physical health (operationalised as all-cause emergency hospital admissions, cardiovascular emergency admission in 65+yr, respiratory emergency admission in 65+yr, emergency admission injuries falls/burns in 65+yr (any place of occurrence), asthma emergency admission (all ages, 65+yr), all-cause A&E attendance (all ages, 0-14yr, 65+yr)); ASB, population turnover, £ rent.
  - o Individual level: self-reported anxiety (primary outcome); general self-reported health, residential stability (ONS Annual Population Survey APS).

### 8c. Purpose

Mixed-methods evaluation of impacts and processes. The impact assessment intends to estimate causal effects.

# Part C: METHODS

# 9. Design and setting of study

# 9a. Study design

### WP1 Impact evaluation: Individual-level outcomes

The impact evaluation has a difference-in-differences design with matched controls. The idea of a difference-in-differences design is to supplement a simple before-after comparison of the outcomes of interest in the treated units with a before-after comparison of the outcomes in a set of control units to remove any changes that would have happened in the absence of the intervention. The underlying assumptions is that in the absence of the intervention the average before-after change would have been the same in the treated units and in the control units, known as the parallel trends assumption.

When considering individual-level outcomes, treated units are private rented sector tenants in LSOAs with SL. Potential control units are individuals who do not live in private rented sector housing or who do not live in LSOA with SL. However, SL might have spillover effects. For example, many SL schemes are set up to tackle anti-social behaviour. If they were effective at addressing anti-social behaviour, individuals in SL areas who do not live in private rented housing might also benefit from SL. Using these individuals as controls might therefore result in underestimating the impact of SL. Similarly, individuals in neighbouring LSOAs who do not have an SL scheme in place might be affected by the SL scheme if, for example, SL leads to displacement of certain types of private sector tenants such as tenants engaged in anti-social behaviour. Using these individuals as controls might result in overestimating the impact of SL.

We therefore use as our controls individuals who live in private rented housing in LSOAs without SL that are not direct neighbours of LSOAs with SL. From among these controls, we choose those individuals who live in LSOAs that we have matched to the treated LSOAs using characteristics of the LSOAs such as proportion of individuals who are under 16, proportion of individuals who are non-white and proportion of households classed as overcrowded.

Our individual-level outcome measures come from repeated cross-sectional data, so each year different individuals are being observed in each LSOA. The starting point for our analysis is the canonical two-way fixed effects regression specification:

$$Y_{iat} = \alpha_a + \varphi_t + \beta D_{at} + \varepsilon_{iat}$$

 $Y_{iat}$  indicates one of our outcome measures for individual i in LSOA a in year t.  $\alpha_a$  is an LSOA effect, which accounts for time-invariant differences between the LSOAs, and  $\varphi_t$  is a year effect, which accounts for changes over time happening in all LSOAs.  $D_{at}$  takes the value 1 if LSOA a is subject to an SL scheme in year t and 0 otherwise.  $\beta$  is the treatment effect, i.e. it captures the impact of the SL scheme. In the special case of only two years t (before and after the intervention) the ordinary least squares (OLS) estimate  $\hat{\beta}$  is equivalent to the difference-in-differences estimate  $\hat{\gamma}$ :

$$\hat{\gamma} = \left( \overline{Y}_{SL,AFTER} - \overline{Y}_{SL,BEFORE} \right) - \left( \overline{Y}_{COMPARATOR,AFTER} - \overline{Y}_{COMPARATOR,BEFORE} \right)$$

 $\bar{Y}_{SL,AFTER}$  is the mean of the outcome measure in the LSOAs with an SL scheme after implementation of the SL scheme and  $\bar{Y}_{SL,BEFORE}$  is the mean before implementation.  $\bar{Y}_{COMPARATOR,AFTER}$  is the mean of the outcome measure in the matched comparator LSOAs in the year after SL was implemented in the SL areas and  $\bar{Y}_{COMPARATOR,BEFORE}$  is the mean in the year before implementation. Unfortunately, this intuitive causal interpretation of the parameter estimate  $\hat{\beta}$  is unlikely to apply in the more general case of more than two years t and the intervention being rolled out over several years. As the implementation of SL schemes is at the discretion of local authorities, they have been rolled out at different times over many years.

In this setting with staggered intervention timing the OLS estimator of  $\beta$  in the canonical two-way fixed effects regression yields an unbiased estimate of the treatment effect only if there is no treatment effect heterogeneity, i.e. if all LSOAs have the same treatment effect and if the treatment has the same effect regardless of how long it has been since the treatment started. The bias occurs because the OLS estimator is a weighted average of comparisons between treated and not-yettreated units as well as between treated and already-treated units. If, for example, the treatment effect gets stronger over time, the parallel trends assumption discussed above does not hold for the latter comparison [27,28].

The recent literature on difference-in-differences has proposed alternative estimators that overcome the problem of the "forbidden" comparison between treated and already-treated units by making transparent exactly which units are being used as comparison [29]. We will apply the Callaway and Sant'Anna estimator as our main method [30]. This estimator allows for arbitrary treatment effect heterogeneity and dynamic effects by deconstructing the estimation of the overall treatment effect into estimation of so-called group-time average treatment effects. We will apply different aggregation schemes to explore the overall effect as well as treatment effect heterogeneity over time and across groups.

To assess the plausibility of the parallel trends assumption, we will examine the trends in the outcome measures for the treatment and control units in the before period by plotting the raw data over calendar time for the treatment and control units, with the treatment units and their matched control units. We will test if the estimated treatment effects for the three years before the intervention are jointly statistically significantly different from zero. Recent reviews discuss the difficulties with formally testing parallel trends as the analysis may be underpowered [29,31]. Analysts are advised to also assess event time plots and to exercise a degree of pragmatism in cases of small deviations from no-effect before the intervention.

If the parallel trends assumption seems implausible, we will use Synthetic Difference-in-Differences (SDID) instead of DiD as the primary method [32,33]. If the parallel trend assumption is plausible, we will use SDID for our primary outcome to assess the sensitivity of our results to the specific method. SDID finds controls matched on the pre-intervention evolution of outcomes through a weighting strategy and thereby ensures parallel trends in the pre-intervention period. Simulations have shown that SDID performs well compared to other commonly used methods [34]. We will use the same set of LSOA-level covariates for the synthetic controls as for the propensity score matching (see Table 4).

We will explore spillover effects by repeating the difference-in-differences analysis with matching for (1) individuals who do not live in private rented sector housing and (2) for individuals who live in LSOAs that are first-order neighbours of SL areas. For (1) we will compare individuals who do not live in private rented sector housing in SL areas to individuals who do not live in private rented sector housing in the control areas that we have matched to treatment areas for the main analysis. For (2) we will treat the first-order neighbours of treated LSOAs as if they are intervention LSOAs and match

them to comparable LSOAs that are neither SL areas nor SL area neighbours. We will report the average effects over the first five years after the intervention (0 to 5 years) as the main result. We will report this together with an event time plot showing all available years before and after the interventions. In addition, we will report delayed effects and longer-term effects as secondary results.

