In 2019, UK government published an independent evidence review of selective licensing, which focused primarily on barriers and facilitators to implementation [9]. We have also searched the literature on health outcomes for housing interventions in PRS. We identified 24 studies, around a third of which focused specifically on selective licensing. These were small-scale evaluations with some useful qualitative findings on implementers' views. There was much less evidence on tenant and landlord views, and no robust quantitative evaluation of the impacts (including health, social and economic impacts) of SL, except for our own recently published evaluation. Our own London study is, to our knowledge, the first and only impact evaluation of SL in the available literature.

Our previous study piloted methods and access to data relevant to this study and found our approach feasible. We found reductions (i.e. improvements) in Small Area Mental Health Index (SAMHI) scores; reductions in police-recorded ASB; and increases in population turnover. The findings are promising but focus on impacts within London's unique housing context. Furthermore, sensitivity analysis revealed that the impacts on SAMHI were driven by changes that occurred in London's largest SL, which was also the main setting for the 2012 London Olympics. The ASB and population turnover impacts remained significant even after we omitted this scheme from the analysis. We also found that although SL schemes have 5-year cycles, impacts began to occur from years 3 to 4. If SL schemes can have important impacts prior to completion, this suggests that the schemes may still be impactful even if they achieve only partial compliance and partial completion. It is important to test if these and other impacts occur at the national level.

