### Sub-Group Analysis

We will repeat our analyses of individual- and area-level outcomes for the following subgroups:

• Small versus larger SL schemes. We propose this partly because the larger schemes have been politically contentious (following the change of government in 2024, changes were announced to make it easier for LAs to set up large schemes without needing national government permission), and partly because we hypothesise that resident displacement occurs less in larger schemes – particularly where the schemes extend across the whole local authority area. For this purpose, we will define larger schemes as those covering 90%+ of the Local Authority population (Census 2011): 2012\_Newham, 2014\_BarkingandDagenham,

2015\_Croydon, 2015\_Liverpool, 2015\_WalthamForest. Small schemes will in this analysis be defined as those covering up to 20% of the population. Schemes of intermediate sizes will be ignored in this analysis.

London versus outside London. Comparisons with London are useful because it has a unique housing market and some of its areas were settings for the Olympic Games (a potential confounder).

To examine impacts on equity, we will run the following area-level subgroup analyses by ranking local authorities:

- **Level of deprivation**: lower half (least deprived), upper half (most deprived)
- Proportion of population from a Non-White ethnic background: lower half (low proportion), upper half (high proportion)
- **Proportion of population under 16**: lower half (low proportion), upper half (high proportion)
- Proportion of population over 75: lower half (low proportion), upper half (high proportion)

APS includes items that are relevant to the following equity dimensions covered in the PROGRESS+ framework: Place of residence (which we operationalise as region); Ethnicity, Occupation, Gender, Religion, Education as well as participants who live on their own and participants with child dependents. Occupational status and education can be considered proxies for socio-economic status. Furthermore, the survey asks about long term and limiting health conditions, allowing us to consider these dimensions of disability. It also asks about cohabiting same sex partners. We will incorporate these dimensions into the equity analysis where sample sizes allow us to do so.

To address potential multiple testing issues with the secondary analyses, will adjust the significance tests according to a Benjamini-Hochberg False Discovery Rate of 5% [58].

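### The individual-level analysis has no person-level covariates and no check on tenant composition, so a change in who rents after licensing would be counted in the effect on anxiety

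*Protocol*

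**What the plan says.** Section 9a (WP1, individual-level outcomes; same text in the SAP) describes the outcome data as repeated cross-sections, "so each year different individuals are being observed in each LSOA". It goes on: "The starting point for our analysis is the canonical two-way fixed effects regression specification". That equation has an LSOA effect, a year effect, a treatment indicator and an error term, and nothing about the person. Then: "We will apply the Callaway and Sant'Anna estimator as our main method". No covariates are named for it. Controls are private tenants in areas "matched to the treated LSOAs using characteristics of the LSOAs", and synthetic difference-in-differences (SDID) is to use the same area-level variables.

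The protocol also sets out ways in which licensing could change who rents. Section 7c hypothesises price displacement, landlords leaving the market, discriminatory use of antisocial-behaviour conditions, and displacement of antisocial tenants. Section 9a bars neighbouring LSOAs from the control group because some kinds of tenant might be moved into them. Section 7b reports that the London pilot found "reductions in police-recorded ASB; and increases in population turnover".

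Section 18 (Sub-Group Analysis) lists the person characteristics that the APS holds, among them "Ethnicity, Occupation, Gender, Religion, Education as well as participants who live on their own and participants with child dependents", and assigns them to equity analyses where sample size permits. Years at current address is a separate secondary outcome (Section 14a). Individual-level placebo outcomes are still to be chosen (Section 17). Both documents are silent on person-level adjustment; neither argues against it.

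**The concern.** In a panel of the same people, a person cannot change sex or ethnic group between waves. In repeated cross-sections, the treated sample before and after licensing can be made up of different kinds of tenant. The LSOA effect absorbs only what is constant in an area, so a change in tenant mix that follows licensing is attributed to the treatment term. Section 9a guards the control side against displaced tenants but has no counterpart for the treated side, which those tenants would have left.

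Two results are exposed: the primary individual-level outcome, and the APS life-satisfaction effect. WP3 converts the latter to an income equivalent and multiplies it by the number of people affected. Private tenants in the scheme areas numbered 777,688 (Section 18, Table 2), so any per-person artefact carries in proportion into the benefit total.

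**Working it through.** **1. The plan's own figure.** Section 11, Table 1 gives power 0.837 for N = 1,000 and 30% of an SD. For a two-period difference-in-differences with unit SD, SE = sqrt[2(1/n_treated + 1/n_control)].
- N as treated units, as captioned: sqrt[2(1/1000 + 1/3000)] = 0.0516; 0.30/0.0516 = 5.81; power above 0.999. Not reproduced.
- N as all units, split 3:1: sqrt[2(1/250 + 1/750)] = 0.1033; 0.30/0.1033 = 2.90; power 0.828. This reading agrees within 2 points in 84 of 95 cells.

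The caption is a separate matter, and the point here does not rest on it. The table is used only for scale: about 10% of an SD is detectable at N = 8,000. If instead 8,000 treated respondents divide evenly before and after (an assumption), SE = sqrt[2(1/4000 + 1/12000)] = 0.0258 and the detectable difference is 2.80 x 0.0258 = 7.2% of an SD. Both ignore clustering.

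**2. Where a shift in mix goes.** Let a group of tenants have high-anxiety prevalence g above the rest, and let its share change by d_T in treated and d_C in control areas. With no true effect:
- treated change = year effect + g x d_T
- control change = year effect + g x d_C
- estimate = g x (d_T - d_C) = g x s, where s is the net shift.

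Before the start date s = 0, so the joint test on the three pre-licensing years has nothing to find. SDID weights are fitted to pre-licensing outcomes, and the area covariates are fixed values from about 2011 to 2015, so neither responds to a later shift.

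**3. Size, on assumed inputs.** The documents give neither s nor g.
- 5 points x 10 points = 0.5 percentage points
- 10 x 10 = 1.0
- 10 x 15 = 1.5

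With assumed prevalence of 20%, the SD is sqrt(0.2 x 0.8) = 0.40, so these are 1.25%, 2.5% and 3.75% of an SD. For 1.0 point the figure is 2.8% at 15% prevalence and 2.3% at 25%.

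Simulation of the 10 x 10 case (400 data sets, true effect 0, 4,000 treated per period, 3:1 controls) gave -1.05 points with 18% false rejections unadjusted. With the shifting characteristic in the regression it gave -0.05 points and 4.5%. The sign reflects only the direction chosen for the shift. Clustering would lower the rejection rates but not the bias.

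**4. Which adjustment works.** Suppose the outcome model in controls is m_C,t(X) = a_t + gX. An estimator that models only control outcomes computes the raw treated change minus the treated-sample average of m_C,post(X) - m_C,pre(X). That bracket equals a_post - a_pre for every X, so g x s stays in the treated change. Simulations of the 10 x 10 case gave -0.99 and -0.98 points, against -1.00 and -0.98 unadjusted. Fitting models in all four cells (treated and control, before and after) and averaging over one distribution of X cancels the shift: 0.01 and 0.02 points. Where the shift was on a trait not in the model, -1.0 point remained after adjustment.

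**5. Could the composition check see such a shift?** The SD of a share is at most 0.5, so on the even split the detectable shift is at most 0.0723 x 0.5 = 3.6 points before clustering. A 5-10 point shift on a measured characteristic would therefore be visible if clustering is modest.

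**The case against.** The strongest reply concerns the estimand. Section 9a defines treated units as private tenants in licensed areas, whoever they are in that year. On that reading a changed mix is part of what licensing does, and adjustment answers a different question. This stands: it is why the unadjusted estimate should stay. But the population in Section 8b is individual tenants exposed to licensing, and WP3 treats the estimate as a gain per person, so the plan needs to say which it means.

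The mechanisms are hypotheses, not forecasts. The pilot's turnover index covers all residents of an area, and more movement is not a different mix. Section 18 expects less displacement in larger schemes, and the five it names hold 155 + 110 + 220 + 298 + 144 = 927 of 1,635 treated LSOAs (57%), or 68% of the 1,356 fully covered ones. All of this tempers the likely size.

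There are partial safeguards: residential stability, turnover, the scheme-size comparison, and subgroup analyses that hold one trait fixed. They may signal movement but do not correct or qualify the anxiety estimate. The equation is called a starting point and the estimator can take covariates, but none is specified.

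Three stronger readings are tempting. A reader might infer that licensing could look beneficial by pushing out anxious tenants, but nothing in the documents links displaced tenants to higher anxiety. A reader might infer that adjusting for age, sex and ethnicity would cure the problem. Yet the hypothesised mechanisms sort largely on ability to pay and antisocial behaviour, which those variables do not measure. Or a reader might conclude that the main analysis must be replaced; while the estimand is unstated, that does not follow.

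**Conclusion.** The gap is real. No person-level term appears in the model, the matching or SDID, nothing tests APS composition, and the planned pre-trend checks cannot detect a shift that begins with licensing. The 0.5-1.5 point illustration rests wholly on assumed inputs. It is below the roughly 3.6-4.3 points that 10% of an SD represents at 15-25% prevalence, so by itself it would seldom produce a significant result. It would still move the point estimate, and an artefact of the same kind in life satisfaction would carry undiluted into WP3. This is a change worth making before outcome analysis, chiefly because it decides whether the result can be described as an effect on individual tenants.

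**What to change.** 1. State whether the individual-level estimand is the effect on exposed tenants at fixed composition or the effect on the changing pool of tenants.
2. Run the same difference-in-differences with characteristics that licensing cannot change for a person as outcomes: sex, ethnicity, and age if available.
3. For anxiety and life satisfaction, report beside the unadjusted estimate a pre-specified covariate-adjusted repeated-cross-section estimate. Name the estimator version, with outcome models fitted in treated as well as control cells, before and after.
4. Pre-specify that, if composition changes or the two estimates differ, the unadjusted estimate and the WP3 benefit built on it are not interpreted as an effect on individual tenants.
5. State that adjustment covers measured mix only, not income or antisocial behaviour.

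A restriction to respondents whose years at address pre-date the scheme should be omitted or labelled exploratory, because Section 14a treats years at address as something licensing may alter.

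The cost is SAP wording and extra model runs, mostly on variables that Section 18 already lists. Some records would be lost under the complete-case rule in Section 19, and precision would fall slightly. The SAP's introduction requires later changes to be justified publicly, so this is best settled before outcome analysis begins.

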#### WP1 Impact evaluation: Area-level outcomes

When considering area-level outcomes, treated units are LSOAs with SL. Potential control units are LSOAs without LSOA. However, SL might have spillover effects. Neighbouring LSOAs who do not have an SL scheme in place might be affected by the SL scheme if, for example, SL leads to displacement of certain types of private sector tenants such as tenants engaged in anti-social behaviour. Using these LSOAs as controls might result in overestimating the impact of SL. We therefore use as our potential controls LSOAs without SL that are not direct neighbours of LSOAs with SL. From among these potential controls, we choose LSOAs that we have matched to the treated LSOAs using characteristics of the LSOAs such as proportion of individuals who are under 16, proportion of individuals who are non-white and proportion of households classed as overcrowded.

The starting point for our analysis of the area-level outcomes is the following two-way fixed effects regression specification:

$$Y_{at} = \alpha_a + \varphi_t + \beta D_{at} + \varepsilon_{at}$$

 $Y_{at}$  indicates one of our outcome measures for LSOA a in year t.  $\alpha_a$  is an LSOA effect, which accounts for time-invariant differences between the LSOAs, and  $\varphi_t$  is a year effect, which accounts for changes over time happening in all LSOAs.  $D_{at}$  takes the value 1 if LSOA a is subject to an SL scheme in year t and 0 otherwise.  $\beta$  is the treatment effect, i.e. it captures the impact of the SL scheme. Because of the staggered intervention timing we will apply the Callaway and Sant'Anna estimator and estimate all relevant group-time average treatment effects and then summarise them using different aggregation schemes [30].

As for the individual-level outcomes, we will assess the plausibility of the parallel trends assumption by examining the trends in the outcome measures for the treatment and control units in the before period by plotting the raw data and by running an event study regression for each group. In case the parallel trends assumption is implausible, we will use Synthetic Difference-in-Differences (SDID) instead of DiD as the primary method [32,33].

We will explore spillover effects by repeating the difference-in-differences analysis with matching for LSOAs that are first-order neighbours of SL areas by treating the first-order neighbours of treated LSOAs as if they are intervention LSOAs and matching them to comparable LSOAs that are neither SL areas nor SL area neighbours.

